10.2.2 Adverse event reporting period

All adverse events, regardless of severity, causality or seriousness must be reported from the date of informed consent until the end of the study or 28 days after the last dose of study medication, whichever is later. However, any adverse event that the investigator believes is at least possibly related to study medication should be reported regardless of time elapsed from the final dose.

10.3 Serious adverse events

10.3.1 Serious adverse event definition

A **serious adverse event** (SAE) is defined as follows:

Any adverse drug experience occurring at any dose that results in any of the following outcomes:

- death
- life-threatening situation (subject is at immediate risk of death)
- inpatient hospitalisation or prolongation of existing hospitalisation (excluding those for study therapy or placement of an indwelling catheter, unless associated with other serious events)
- persistent or significant disability/incapacity
- congenital anomaly/birth defect in the offspring of a subject who received study product
- Other: Important medical events that may not result in death, be immediately life-threatening, or require hospitalisation, may be considered a SAE when, based upon appropriate medical judgment, they may jeopardise the subject and may require medical or surgical intervention to prevent one of the outcomes listed in this definition. Examples of such events are:
 - intensive treatment in an emergency room or at home for allergic bronchospasm
 - blood dyscrasias or convulsions that do not result in hospitalisation
 - development of drug dependency or drug abuse

10.3.2 Clarification of serious adverse events

Death is an outcome of an AE, and not an AE in itself. In reports of death due to “Disease Progression”, where no other information is provided, the death will be assumed to have resulted from progression of the disease being treated with the study product(s).

All deaths, regardless of cause, must be reported to Sponsor for subjects on study and for deaths occurring within 30 days of dosing of last study drug or within 30 days of last study evaluation, whichever is longer.

“Occurring at any dose” does not imply that the subject is receiving study drug at the time of the event. Dosing may have been given as treatment cycles or interrupted temporarily prior to the onset of the SAE, but may have contributed to the event.

“Life-threatening” means that the subject was at immediate risk of death from the event as it occurred. This does not include an event that might have led to death, if it had occurred with greater severity.

Complications that occur during hospitalisations are AEs. If a complication prolongs hospitalisation, it is a SAE.

“In-patient hospitalisation” means the subject has been formally admitted to a hospital for medical reasons, for any length of time. This may or may not be overnight. It does not include presentation and care within an emergency department.

The Investigator should attempt to establish a diagnosis of the event based on signs, symptoms and/or other clinical information. In such cases, the diagnosis should be documented as the AE and/or SAE and not the individual signs/symptoms.

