10.2.1 Assessment of AEs

All AEs will be assessed by the Investigator and recorded on the appropriate CRF page, including the date of onset and resolution, severity, relationship to study product, outcome and action taken with study medication. See Appendix 1 for details of the NCI CTCAEv4.03 toxicity grading scale.

In addition, injection site reactions will be graded by an Investigator or designee, according to severity. It is anticipated that the subjects may find it difficult to differentiate pain and tenderness and for this reason pain and tenderness have been combined in the following grading scale:

Table 7 – Grading for Pain and Tenderness at injection sites

Mild Grade 1	Moderate Grade 2	Severe Grade 3
Awareness of symptoms but easily tolerated	Discomfort enough to cause interference with usual activities	inability to do work or usual activities

For all other reported adverse events, severity should be recorded and graded as:

Grade	Severity	Comments
1	Mild	Aware of sign or symptom, but easily tolerated. Concomitant medication is not ordinarily indicated for relief of mild AEs
2	Moderate	Discomfort enough to cause interference with usual activities. Concomitant medication may be indicated for relief of moderate AEs
3	Severe	Incapacitating with inability to work or perform usual activities. Concomitant medication may be indicated for relief of severe AEs

The relationship to study drug should be assessed using the following definitions:

Causality	Comment
Unrelated	AE is clearly due to extraneous causes (e.g. underlying disease, environment, known effect of another drug)
Unlikely	The temporal association between the AE and study drug is such that study drug is not likely to have any reasonable association with the AE
Possible	The AE could have been produced by the subject's clinical state or study drug
Probable	The AE follows a reasonable temporal sequence from the time of study drug administration, abates upon discontinuation of the study drug and cannot be reasonably explained by the known characteristics of the subject's clinical state
Definite	The AE follows a reasonable temporal sequence from the time of study drug administration, abates upon discontinuation of the study drug and/or reappears when study drug is re-introduced

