These criteria in addition to good clinical judgment should be used as a guide for determining the causal assessment. If it is felt that the event is not related to study product, then an alternative explanation should be provided.

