10.3.3.2 Investigator reporting requirements for SAEs

An SAE may qualify for reporting to regulatory authorities if the SAE is considered to have a possible causal relationship to the study product, and is unexpected (Suspected Unexpected Serious Adverse Reaction [SUSAR]) based upon the current Investigator's Brochure. In this case for multi-centre studies, all Investigators will receive a formal notification describing the SAE.

Where this is required by local regulatory authorities, and in accordance with the local institutional policy, the Investigator should notify (in writing) the Human Research Ethics Committee (HREC) which approved the study of the SAEs, according to HREC requirements as soon as is practical.

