For any subject experiencing any event (irrespective of severity) which, in the opinion of the Investigator, contraindicates further dosing in that subject and the event is considered to be at least possibly related to treatment (or where causality to study treatment cannot be ruled out – see Section 10.2.1), continued dosing of the subject should be interrupted. In all cases, the final treatment decisions, made in response to toxicity, are the responsibility of the Investigator. A careful evaluation of the potential risk/benefit will dictate the optimal therapeutic course. Should treatment be interrupted, re-initiation will follow review of the available safety data and in agreement with the Sponsor. There will be no dose reduction or modification.

If the Investigator deems that management of the patient's medical condition requires knowledge of the study treatment regimen, then the Medical Monitor must be contacted for consultation and the procedures described in Section 7.3 followed. If a patient dies from an event that is considered to be at least possibly related to treatment, continued dosing of all study participants should be interrupted until the SMC has reviewed the data.

Clinically significant suspected adverse drug reactions, and serious adverse events considered to be related to study procedures will be followed until resolved or considered stable. All subjects who experience a study drug related AE should be followed until resolution of the AE, even if the subject has discontinued study drug.

If an unscheduled interruption of study drug occurs, the study site should notify the Sponsor at the earliest possible time. In the event that a subject requires an unscheduled interruption of study drug under conditions other than those associated with toxicity, the case will be reviewed by the Sponsor to determine whether such a subject will be allowed to resume study drug.

Subjects withdrawn from study drug will be treated as deemed appropriate by the Investigator. Follow-up procedures should be performed and the appropriate CRFs should be completed.

The study may be terminated at any point in time at the discretion of the Sponsor.

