10.8 Warnings and precautions

This is a first in man study of DEN-181 so the adverse event profile is not characterised and cannot be reliably predicted. The preclinical data suggest an acceptable safety profile and a safety margin in excess of 10x is associated with the highest dose selected for study. Facilities and staff for resuscitation and treatment of other medical emergencies will be provided if required

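### Section 10.3.2 presumes that a sparsely documented death reported as disease progression was due to RA, which can feed an Unrelated rating without evidence

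*Protocol*

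**What the plan says.** Section 10.3.2 of the Protocol deals with deaths reported as due to disease progression and without other information. For these, "the death will be assumed to have resulted from progression of the disease being treated with the study product(s"). The disease being treated is RA.

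Four other parts of the Protocol bear on what follows from that.

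- **Causality rating (10.2.1).** "All AEs will be assessed by the Investigator and recorded on the appropriate CRF page", including the relationship to study product. There are five categories. Unrelated means "AE is clearly due to extraneous causes (e.g. underlying disease, environment, known effect of another drug"). Possible means "The AE could have been produced by the subject's clinical state or study drug". The section adds: "If it is felt that the event is not related to study product, then an alternative explanation should be provided".
- **Pause after a death (10.7).** "If a patient dies from an event that is considered to be at least possibly related to treatment, continued dosing of all study participants" is to be interrupted until the Safety Monitoring Committee (SMC) has reviewed the data.
- **Regulatory reporting (10.3.3.2).** A serious adverse event may qualify if it is "considered to have a possible causal relationship to the study product" and is also unexpected.
- **State of knowledge (10.8).** "This is a first in man study of DEN-181 so the adverse event profile is not characterised and cannot be reliably predicted".

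RA worsening is itself a safety outcome. Section 4.2.1 places exacerbation of RA under the primary endpoints, assessed by DAS28CRPv4, and section 10.1 lists RA severity among the safety parameters.

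**The concern.** The sentence settles a cause of death because information is missing. In a trial of an established drug for a disease that is often fatal in the short term, that might be a harmless convention. Here it is a poor default for three reasons.

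First, the product is being given to humans for the first time, and it delivers an RA-associated self-antigen (3.2). The intent is tolerance, but the Protocol cannot know in advance that progression of RA is independent of the product. It says as much in 10.8, and it measures RA exacerbation as a possible harm.

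Second, progression of RA is not an obvious cause of death in this population over this period. Participants are followed for 56 days after first dosing (5.1), may enter with no swollen joints (6.2), and in Part B must have been diagnosed within the previous 2 years (6.3.1). Section 3.1 attributes the reduced survival in RA to cardiovascular complications.

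Third, two safeguards depend on the relatedness judgement that the presumption may influence. At stake is an unbiased causality rating for the most serious event that the trial can record.

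**Working it through.** No arithmetic applies: the Protocol gives no figure on this point, and the question is whether one rule leads to another. I took the links in turn.

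1. **Does the Protocol presume RA as the cause?** Yes. The wording in 10.3.2 is mandatory, but it applies only where the report already names disease progression and says nothing more. It does not cover unexplained deaths in general.

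2. **Does the presumption make the death Unrelated?** Not by itself. Section 10.3.2 speaks of cause and names no category. Under 10.2.1 the Investigator decides, Unrelated needs a cause that is clearly extraneous, and a cause assumed for lack of information is not clear. Possible expressly includes events that either the clinical state or the drug could have produced.

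3. **Can it lead there?** Yes. Underlying disease is the first example given under Unrelated, and 10.2.1 asks for an alternative explanation whenever an event is judged not related. The presumption supplies that explanation ready-made. An Investigator who follows 10.3.2 literally could complete the form as Unrelated with no evidence beyond the two words on the report.

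4. **What depends on the rating?**
   - The pause in 10.7 for all participants. It is the only trial-wide pause in the Protocol that is tied to a death. The other stopping sentence in 10.7 turns on suspected reactions or on changes that pose a significant health risk, not on a death. The ad hoc SMC meetings in section 11 carry no stated pause.
   - Regulatory reporting of suspected unexpected serious reactions in 10.3.3.2.
   - The tabulation of adverse events by relationship to study drug in 13.6.4.

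5. **What does not depend on it?**
   - Section 10.3.2 sends all deaths to the Sponsor whatever the cause.
   - Section 10.3.3.1 requires every serious adverse event to be reported within 24 hours regardless of causality. Hospital and autopsy reports follow for fatal events when requested, and the Sponsor may ask for more.
   - The primary adverse event analysis in 13.6.4 counts treatment-emergent events without filtering on relatedness. It also provides for on-study deaths in tables and/or listings.

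6. **Is the presumption consistent with the rest of the safety plan?** Not comfortably. Section 10.2 counts a pre-existing condition that worsens as an adverse event, and 4.2.1 and 10.1 treat worsening RA as a safety outcome. Section 10.3.2 treats fatal worsening as accounted for by the disease.

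Links 1 and 3 hold on the text, and so do the dependencies in step 4. Link 2 holds only as a risk.

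**The case against.** The strongest reply is that the sentence does very little. Someone has already reported progression as the cause, and the sentence merely says which disease is meant. It leaves causality with the Investigator, who can still choose Possible and is told in the same section to try to establish a diagnosis. Notification does not depend on relatedness, the SMC meets at once on any safety concern, and its decision rules sit in a charter that is not at hand.

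Most of that stands, and it rules out several stronger readings:

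- A reader might infer that the presumption automatically makes the death Unrelated and disables the pause in 10.7. The text does not say so, because no category is assigned and Possible stays open.
- A reader might infer that the less is known about a death, the less it will be reviewed. The reporting rules in 10.3.2 and 10.3.3.1 apply regardless of cause.
- A reader might see a conflict with the sentence in 10.7 on events whose causality cannot be excluded. That sentence concerns further dosing of a single participant, not deaths.
- A reader might think that the primary safety endpoint is decided in the drug's favour. Section 13.6.4 removes no death from the analysis.

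The reply does not justify keeping the sentence. If it only names the disease, nothing is lost by deleting it. If it does more, it steers a judgement that ought to rest on evidence. The SMC is a partial backstop: under section 11 it sees only data blinded to allocation, and its members include the Investigator(s), who rate causality.

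**Conclusion.** The point holds in a limited form. The presumption in 10.3.2 can supply, without evidence, the explanation needed for an Unrelated rating. It may therefore keep the pause in 10.7 and the reporting in 10.3.3.2 from being considered. It is also out of keeping with a first-in-human trial in which RA exacerbation is a safety endpoint.

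The size cannot be expressed as a number. The Protocol gives no basis for how often a death would be reported as bare disease progression, and the event is likely to be rare. What could change is the relatedness rating and whatever follows from it. Notification of the death and its place in the safety output are unaffected.

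The conclusion assumes that an Investigator might read 10.3.2 as bearing on causality, and that the SMC Charter contains no separate rule for deaths. Such a rule would reduce the practical effect but would not cure the inconsistency within the Protocol. The correction should be made, but the primary analysis does not depend on it.

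**What to change.** Delete the presumption from 10.3.2. In its place, state that when a death is reported as disease progression without other information, further information is sought. The Investigator then assesses cause and relatedness individually, using the five existing categories in 10.2.1. No new causality category is needed.

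Reconcile 10.3.2 with 4.2.1, 10.1, 10.2.1, 10.3.3.2 and 10.7, so that fatal worsening of RA is handled in the same way as other worsening of RA. No change to the dosing rule in 10.7 is proposed.

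The cost is one or two sentences in an amendment, and occasionally some extra follow-up or a committee review of a death that proves unrelated.

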10.3.3 Serious adverse event reporting requirements

10.3.3.1 All SAEs

The Sponsor has responsibilities for expedited reporting of SAE's meeting specific requirements to worldwide regulatory authorities; therefore, all appropriate parties must be notified immediately regarding the occurrence of any SAE that occurs after the first dose of study product or placebo has been administered. The procedures for reporting all SAEs, regardless of causal relationship, are as follows:

- Complete the "Serious Adverse Event Report" CRF page
 - Email the SAE report to the CRO SAE email address within 24 hours of the Investigator's knowledge of the event at the numbers below [Please refer to the Study Reference Manual for the designated email address]
 - for fatal or life-threatening events, also fax copies of hospital case reports, autopsy reports, and other documents when requested and applicable

The Sponsor may request additional information from the Investigator to ensure the timely completion of accurate safety reports.

The Investigator must take all therapeutic measures necessary for resolution of the SAE. Any medications necessary for treatment of the SAE must be recorded onto the concurrent medication section of the subject's CRF.

10.3.3.2 Investigator reporting requirements for SAEs

An SAE may qualify for reporting to regulatory authorities if the SAE is considered to have a possible causal relationship to the study product, and is unexpected (Suspected Unexpected Serious Adverse Reaction [SUSAR]) based upon the current Investigator's Brochure. In this case for multi-centre studies, all Investigators will receive a formal notification describing the SAE.

Where this is required by local regulatory authorities, and in accordance with the local institutional policy, the Investigator should notify (in writing) the Human Research Ethics Committee (HREC) which approved the study of the SAEs, according to HREC requirements as soon as is practical.

10.4 Follow up of serious and non-serious adverse events

Follow-up of serious and non-serious AEs will continue through the last day on study (including the follow-up, off study medication period of the study), until the Investigator and/or the Sponsor determine that the subject's condition is stable, or up to 30 days after the last dose of Study Product, whichever is longer. The Sponsor may request that certain AEs be followed until resolution.

10.5 Clinical Laboratory Abnormalities and Other Abnormal Assessments as AEs or SAEs

All laboratory values must be reviewed in real time by the Investigator. Given that all laboratory data are collected and statistically analysed according to their respective toxicity gradings, laboratory abnormalities that occur without related clinical symptoms and signs should generally not be recorded as AEs unless they represent a clinically significant event. Where possible, the overall diagnosis rather than the laboratory abnormality should be recorded on the AE CRF. This will avoid duplication of laboratory abnormalities in both the AE and laboratory reports. Abnormal laboratory results that are of clinical significance should be reviewed by the Medical Monitor.

Any laboratory test result that meets the criteria for a SAE (refer to Section 10.3) should be recorded as an AE, the AE page of the CRF completed and a SAE form also completed in order for the sponsor to collect additional information about that abnormality, including information regarding relationship to study product or other causes, any action taken and resolution.

10.6 Toxicity Management

AEs and abnormal laboratory values, if appropriate, should be graded according to the NCI CTCAE v4.03 grading scale (Appendix 1). Where parameters are not addressed within the TGS, laboratory abnormalities should be assessed as “Clinically Significant” or “Not Clinically Significant”. All abnormal values should be confirmed by repeat testing as soon as possible, preferably within 3 calendar days of receipt of results prior to dose interruption or discontinuation, unless such a delay is not consistent with good medical practice.

For the purpose of monitoring toxicities, the baseline value is defined as the last value prior to the administration of the first dose of study product. This value must be obtained from the local laboratory. All management is based on changes from this value.

All results that are classified as “Clinically Significant” should be documented in the AE form of the CRF.

10.7 Guidance for dose modification or discontinuation of treatment

To date, no specific toxicities have been identified that result from DEN-181 treatment. Any toxicities and/or abnormal laboratory findings should be investigated for aetiology and graded according to Appendix 1.

The following toxicity management will be followed:

- Grade 1 or 2: Patients may continue study treatment/placebo (except if they have an elevated temperature of >38 degrees Celsius or inter-current systemic illness). Dosing may be delayed for up to 7 days. Any dosing delays of >7 days may require that the subject is withdrawn after discussion with the Medical Monitor. Safety assessments will occur immediately prior to each dosing of IMP;
- Grade 3: Patients with any Grade 3 toxicity considered to be at least possibly related to treatment (i.e. treatment related events) should be evaluated carefully by the Investigator prior to continuing IMP treatment. Investigators may discuss individual cases with the Medical Monitor;
- Grade 4: Patients developing any Grade 4 toxicity should have treatment interrupted. The Investigator should contact the Medical Monitor to discuss the subject’s withdrawal.

Subjects will be withdrawn from treatment permanently should any of the following occur:

- Treatment related Grade 4 toxicity
- The need to take medication which could interfere with study measurements
- Subject unwilling to proceed and/or consent is withdrawn.

Where possible subjects who are withdrawn from treatment will remain on the study and attend the scheduled study visits, provided the Investigator deems it appropriate and the Sponsor approves.

Dosing will be stopped if suspected adverse drug reactions, changes to vital signs or clinical laboratory results are observed and these changes pose a significant health risk.

A corresponding adverse event will be captured within the CRF.

For any subject experiencing any event (irrespective of severity) which, in the opinion of the Investigator, contraindicates further dosing in that subject and the event is considered to be at least possibly related to treatment (or where causality to study treatment cannot be ruled out – see Section 10.2.1), continued dosing of the subject should be interrupted. In all cases, the final treatment decisions, made in response to toxicity, are the responsibility of the Investigator. A careful evaluation of the potential risk/benefit will dictate the optimal therapeutic course. Should treatment be interrupted, re-initiation will follow review of the available safety data and in agreement with the Sponsor. There will be no dose reduction or modification.

If the Investigator deems that management of the patient's medical condition requires knowledge of the study treatment regimen, then the Medical Monitor must be contacted for consultation and the procedures described in Section 7.3 followed. If a patient dies from an event that is considered to be at least possibly related to treatment, continued dosing of all study participants should be interrupted until the SMC has reviewed the data.

Clinically significant suspected adverse drug reactions, and serious adverse events considered to be related to study procedures will be followed until resolved or considered stable. All subjects who experience a study drug related AE should be followed until resolution of the AE, even if the subject has discontinued study drug.

If an unscheduled interruption of study drug occurs, the study site should notify the Sponsor at the earliest possible time. In the event that a subject requires an unscheduled interruption of study drug under conditions other than those associated with toxicity, the case will be reviewed by the Sponsor to determine whether such a subject will be allowed to resume study drug.

Subjects withdrawn from study drug will be treated as deemed appropriate by the Investigator. Follow-up procedures should be performed and the appropriate CRFs should be completed.

The study may be terminated at any point in time at the discretion of the Sponsor.

